# February 16, 2018

## Cardio training of older adults with central obesity

### Background

More than 2.8 million people die each year due to obesity or being overweight and excess bodyweight constitute the fifth largest risk factor for death globally(1). Given its increasing prevalence, effects on socioeconomic costs and the ever growing list of illnesses related to obesity there is need for more effective, preventative strategies(2). Primary intervention and changes in life-style can help to combat obesity but further research is still warranted into causality in order to overcome this diverse problem.

Abdominal obesity is a well-established risk factor for cardiovascular disease (3-6) and all-cause mortality (7). Abdominal obesity is caused by high amounts of visceral adipose tissue (VAT) (5), which is fat located inside the abdominal cavity (6). Other risk factors include metabolic syndrome (8), smoking (9, 10) elevated blood lipids (11) and physical inactivity (12).

Further, the interest of the interactions between host and gut microbiota interactions have recently gained a lot of attention as an altered/dysfunctional microbiota have been linked to obesity, ill-health and a growing number of diseases. Recent evidence even suggests that the gut microbiome may play a role in energy balance and could be a mediating factor between obesogenic feeding and the impaired nutrient sensing seen in obesity. (13, 14) Furthermore, the characterization of “normal” microbiota is not firmly established in where the between studies variation is large, suggesting the need for more studies of the bacterial community characterization especially as data on taxonomic and functional changes in the gut microbiota of obese patients are scarce.

Physical activity is a potentially modifiable determinant of both type 2 diabetes (T2D) and obesity. In a systematic review, moderate-intensity physical activity were associated with a 30% lower risk of T2D, although the optimal amount of weekly PA was not determined (15). Patients with obesity or diagnosed with T2D routinely receive recommendations to increase daily PA (e.g. the WHO recommendation of 150 min PA per week). However, present recommendations have been reported to be insufficient to promote a healthy lifestyle (16). It is thus urgent to find better strategies into increasing the level of physical activity in the community.

In summary, interventions targeting older individuals with central obesity and evaluated with high precision measurements has the potential to increase the health and thereby the quality of life of a steadily increasing number of elderly suffering from obesity.

### Methodology

#### Expected outcomes

##### **Primary measured outcomes**

- Visceral adipose tissue as measured by DXA

##### **Secondary measured outcomes**

- Blood lipids
- Blood pressure
- Fasting glucose
- Adiposity (Weight, BMI, waist circumference)
- Physical fitness and functioning (e.g. cardiovascular fitness and muscle strength)
- Resting metabolic rate
- Health-related quality of life (QoL - this includes aspects of psychological well-being and satisfaction)

# February 16, 2018

- Self-reported physical activity (IPAQ)
- Perceived health
- Microbiota composition analysis from stool samples
- Dietary habits

## Plan of investigation

The present research proposal has its origin in an ongoing population-based intervention study, the Healthy Ageing Initiative (HAI) that aims to investigate risk factors for NCDs. The individuals identified as having central obesity within the HAI study will be invited to the present 10-week randomized intervention study.

## **IDENTIFYING INDIVIDUALS ELIGIBLE FOR THE PRESENT INTERVENTION STUDY - short description of HAI**

All individuals residing in the Umeå municipality is invited to HAI when they turn 70 years old. So far, over 3500 individuals have participated in the study with a participation rate over 70%. The participants visit the clinic at 2 occasions a week apart (please see Johansson et al.(17), for further details surrounding the test procedure). At the first visit, traditional and potential novel risk factors for non-communicable diseases are collected, blood samples sent for analyses, and they go home with accelerometers to collect data on physical activity and sedentary behavior. At the one-week follow up visit the participants receive, based on the test results, a tailored intervention aiming at decreasing the risk of diabetes and cardiovascular diseases through counseling regarding main risk factors such as physical inactivity, unhealthy diet, tobacco use and harmful use of alcohol. The basis in the therapy is a cognitive behavioral therapeutics approach using motivational interviewing(18) and prescription-based exercise(19).

We will invite those that have central obesity defined as more than 1 kg for women or 2 kg for men of VAT-mass (approximately 50% of the total cohort) at the visit to HAI. The cut-offs used for VAT mass translates the cut-off values that have been proposed for waist circumference (88 cm for women and 94 for men). Based on visitors from the last 6 month (400 men and women), around 200 will meet the inclusion criteria.

## **Exclusion criteria**

We will exclude participants on basis on conditions that are contraindicated of training or ability to perform the training program. The exclusion criteria are:

- Physical disability which affects ability to perform the exercises of the training program
- Heart failure or severe degenerative condition, e.g. malignant cancer, multiple sclerosis etc.
- myocardial infarction or stroke the last year
- Heart condition that can worsen with aerobic training, e.g. angina pectoris

Any uncertainties regarding participation that may arise during the baseline test anamnesis will be discussed with the physician in charge of the study.

# February 16, 2018

## DESCRIPTION OF THE PROPOSED 10-week RANDOMIZED INTERVENTION STUDY

[figure not shown]

Figure 1. Timeline of the two-step intervention which starts with a traditional randomized controlled trial followed by digitalized form of the intervention that is offered the control group.

### The training program

Participants will train in groups of 10 persons, three times a week for 10 weeks and each session will last for 45-60 min. The training program is developed and led by senior students from the bachelors program of exercise physiology of Umeå University. Each session starts with 5-10 min warmup. The training program will focus on station-based, aerobic exercise with the inclusion of resistance exercises using predominantly only bodyweight as resistance. The intensity of the exercise will be aimed at 60-80% maximal exhaustion and each exercise bout will last for 60 sec with 20 sec rest between bouts.

The program is progressive and individualized, starting the first week at a moderate pace so that the participants can learn the exercises properly. Also, each exercise has different difficulty levels, which makes them easy to individualize and progress in. During the exercises, the participants are instructed to reach 13-17 of the Relative Perceived Exertion Borg scale (RPE Borg)(20), which is a self-assessment scale from 6 to 20 and where 6 is no exertion and 20 is maximal exertion. 13 represent somewhat hard and 17 represents very hard.

If the participants experiences discomfort or light-headedness, they are instructed to pause the activity and consult the instructors before they continue the exercise. Additionally, training bands will be provided to both the instructor led and home-based training group in order to reduce the risks of falls in relation the exercises.

### Anthropometrics

Height and weight are measured and BMI is calculated. Blood pressure is measured with a mercury sphygmomanometer after 5 min rest with the subject in a supine position. Blood samples are collected for analysis of blood glucose, insulin, HbA1c, CRP and blood lipids.

### Body composition

In addition to BMI, body composition is measured with a Lunar iDXA and the CoreScan application (GE Healthcare, Wauwatosa, WI, USA). Using this new software objective measures of visceral fat

# February 16, 2018

mass can be measured in the abdominal region by a computerized algorithm based on the attenuation of the X-ray radiation. By this method we can distinguish visceral fat from the subcutaneous fat that is regarded as more favorable. The results are derived in grams and cubic centimeters. In addition, total fat mass is derived from total body scans, and the amount of gynoid fat is estimated automatically using the region of interest program. Also lean body mass of the total body is measured.

## Isometric muscle strength

Isometric muscle strength of the non-dominant hand is measured using a validated isometric hand dynamometer (Jamar, Lafayette Instrument, USA). The better of two trials will be used in further analysis.

## Physical capacity

Level of aerobic fitness is determined using an electrically braked ergometer cycle using Åstrands submaximal test.

## Stool sample processing and extraction

Stool samples are collected at baseline, 1 week and after 16 weeks intervention for group i and ii. Samples from the 50 non obese subjects (group iii) are only collected at baseline and after 1 week. Stool samples is collected and immediately stored at  $-18^{\circ}\text{C}$ . Bacterial DNA is extracted from fecal samples using the QIAamp DNA Stool mini kit (Qiagen, Germany) according to the manufacturer's protocol.

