## Statistical analysis

Primary analyses will be conducted on an intention-to-treat basis, all participants will be included regardless of whether they completed the follow-up assessment visit. To handle missing data, we will use methodology based on last observation carried forward for participants who did not attend the post-assessment visit. The mean change between pre-intervention and post-intervention measures will be analyzed using the *t*-test when change data are normally distributed otherwise the nonparametric Wilcoxon matched-pairs signed-rank test will be used. Mixed-model analysis will be used to evaluate the change of weight during the intervention to control for relevant covariates. Analyses will be carried out using the SPSS statistical package.

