## Clinical relevance

There are great health gains to be made when overweight persons starts training, including; reduced risk of hypertension and high blood lipids, reduced risk of diabetes and cardiovascular disease. If you already suffer from high blood pressure or diabetes then increased physical activity is a common treatment as it has been shown to improve the condition. Furthermore, after the initial control period, the control group is also offered to receive training and thus the health effects that may arise as a consequence thereof.

Last, there is an urgent need to find an effective, inexpensive and evidence based method to treat patients with central obesity. Hopefully, our study can demonstrate the effectiveness of a digitalized training program that hopefully can be distributed to patients in need of reducing their central obesity towards a healthier life.

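### The last stool sample is timed after 16 weeks of intervention, but the randomised programme is elsewhere 10 weeks long; the sections must be reconciled and the time origin stated

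*Combined protocol and SAP*

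**What the plan says.** The section on stool sample processing and extraction holds the only instruction on when stool is collected: "Stool samples are collected at baseline, 1 week and after 16 weeks intervention for group i and ii". The next sentence adds a group iii of 50 non-obese subjects, sampled at baseline and at 1 week only. Groups i, ii and iii are not defined anywhere else in the readable text.

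The length of the trial is given in three other places, each time as 10 weeks:

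- Plan of investigation: eligible people "will be invited to the present 10-week randomized intervention study".
- The heading of the section on the trial itself: "DESCRIPTION OF THE PROPOSED 10-week RANDOMIZED INTERVENTION STUDY".
- The training program: "three times a week for 10 weeks and each session will last for 45-60 min".

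The caption of Figure 1 describes a randomised trial "followed by digitalized form of the intervention that is offered the control group", and the section on clinical relevance says that "after the initial control period, the control group is also offered to receive training". Neither gives a start week for the controls' training.

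On analysis, the Statistical analysis section says: "The mean change between pre-intervention and post-intervention measures will be analyzed". It mentions "participants who did not attend the post-assessment visit", so one post-assessment visit is foreseen, but it attaches no week to that visit and does not say whether the last stool sample belongs to it. Microbiota composition is listed among the secondary outcomes.

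**The concern.** A sample cannot be taken after 16 weeks of an intervention that lasts 10. Staff who collect stool will work from this sentence, so the conflict is operational and not just a slip in background text.

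At stake is the timing of the only late stool sample. The other two samples per participant are at baseline and 1 week, so neither can stand in for the end of the intervention. If staff count 16 weeks from the start of a 10-week programme, the last sample comes after training has stopped, and perhaps after the control group has been offered training of its own. It would then not measure the difference between the arms at the end of the randomised period, and a sample missed at that time cannot be recovered later.

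**Working it through.** The plan has no calculated figure to reproduce here. The check compares the stated times and works out what each reading implies.

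**Inputs.** Last stool sample: 16 weeks (stool section). Programme length: 10 weeks (Plan of investigation, heading of the trial description, The training program). Frequency: 3 sessions a week (The training program). Stool time points in groups i and ii: 3 (stool section). HAI participants make two clinic visits one week apart (short description of HAI).

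**Step 1: is a 16-week programme described anywhere?** Taken literally, 16 weeks would mean 3 × 16 = 48 sessions, against 3 × 10 = 30 in the training section. No readable text describes the longer programme, an extension of it, or a week-16 visit.

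**Step 2: where does the last sample fall?** Let L be the number of weeks from the origin of the stool clock to the start of training. Training ends at L + 10, so a sample at week 16 falls 16 − (L + 10) = 6 − L weeks after training ends.

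| Reading of the 16 | Gap from end of training to last sample | End-of-intervention stool sample? |
|---|---|---|
| Wrong number; the end of the intervention is meant | 0 weeks | Yes |
| Weeks from the HAI baseline visit | 6 − L; 0 if L = 6 | Yes, if training starts 6 weeks after that visit |
| Weeks from the start of training (L = 0) | 16 − 10 = 6 weeks | No |

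**Step 3: what does the text say for each?**

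- The first reading fits the planned analysis of change from before to after the intervention.
- The second fits the sampling pattern: baseline and 1 week match the two HAI visits, and the non-obese group is sampled at those two times only. Training in groups of 10 could plausibly start some weeks after that visit. The documents give no value for L, and the sentence counts weeks of intervention, so the fit is imperfect.
- The third keeps both numbers but also strains the wording, because the last 6 of the 16 weeks would contain no programme.

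**Step 4: what is exposed under the third reading?** One of the 3 stool time points per participant is misplaced, and it is the only late one. Whether it falls after controls begin training depends on a start week that the readable text does not give. The documents give no microbiota effect size either, so any dilution of a difference between the arms cannot be calculated.

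**The case against.** The strongest reply is that the mismatch may be harmless. Under the first reading only a number needs correcting. Under the second, with a suitable delay before training, the sample already falls at the end of the programme. Figure 1 is the timeline of a two-step scheme that could run past 10 weeks; it may show what week 16 is and who groups i to iii are. Harm needs three things together: the third reading, groups i and ii being the two arms, and controls starting training before the sample. It also concerns a between-arm microbiota comparison that the Statistical analysis section does not specifically describe. Finally, fixing the sample at the end of the randomised period goes further than resolving the conflict requires.

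Most of this stands as a limit on the consequence. None of it removes the conflict in the text, and a timeline that explained week 16 would still leave the stool sentence needing correction. The last objection stands only in part: correcting a number without stating the time origin and the visit could leave the same doubt.

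A reader might infer three stronger things that the documents do not support:

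- **That the microbiota comparison is contaminated by controls who have begun training.** Neither the group definitions nor the start of control training is given.
- **That 10 is right and 16 wrong, because three places outnumber one.** A count of mentions does not settle it.
- **That a known number of samples is affected.** This would require groups i and ii to be the two planned arms of 50, which the text does not say.

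**Conclusion.** The inconsistency is real and should be corrected. The last stool sample is set at 16 weeks of intervention, the programme is given as 10 weeks in three places, and no readable text reconciles them. Confidence is high for the mismatch, but not for any harm.

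The size depends on the reading. Under the first, and under the second if training starts 6 weeks after the HAI baseline visit, the gap is 0 weeks and no contrast is lost. Under the third, the last sample falls 6 weeks after training ends and, if groups i and ii are the randomised arms, there is no end-of-intervention stool sample for the comparison between them. Whether controls would already be training by then is unknown.

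The point concerns one secondary outcome. The sentence says nothing about visceral fat by DXA, so it does not touch the primary outcome.

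**What to change.** 1. Reconcile the stool section with the Plan of investigation, the trial description (including Figure 1) and The training program. Which duration is right is for the sponsor to state.
2. State the week of the last stool sample and its time origin: HAI baseline visit, randomisation or start of training. In the same sentence, say who groups i, ii and iii are.
3. Specify that the stool sample used for the between-arm microbiota comparison is the one taken at the post-assessment visit, at the end of the randomised period and before controls are offered training. Give that visit a week.
4. If a later sample is also wanted, label it as follow-up and do not use it for the end-of-intervention comparison.

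**Cost.** If the 16 is a wrong number, or an unstated count from HAI baseline that already lands at the end of training, only wording changes. If week 16 from the start of training was meant, one sample per participant moves to the post-assessment visit, and the later time point is lost unless an extra sample per participant is kept. Because the plan gives no week for the post-assessment visit, it cannot be assumed that the visit schedule already fits; the sponsor should confirm this.

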## Microbiome sequencing

The purified bacterial DNA will then be analyzed using next generation sequencing (NGS). 16S rRNA gene sequencing is a well-established method for studying phylogeny and taxonomy of samples from complex microbiomes. Unlike capillary sequencing or PCR-based approaches, next-generation sequencing (NGS) is a culture-free method that enables analysis of the entire microbial community within a sample. Samples will be sequenced on the Illumina MiSeq System (San Diego CA, USA).

## Questionnaire

The participants complete a comprehensive questionnaire that covers socioeconomic and psychosocial conditions, self-rated health, personal health history and family history of CVD and diabetes, quality of life, physical activity, tobacco consumption, eating habits and a food frequency questionnaire.

Hospital Anxiety Depression Scale (HADS) is used to measure depression and anxiety(21). In addition SF-36 is used to generate scores for physical and mental health and will be used with SF-6D(22). The SF-6D is a widely used classification for describing health derived from a selection of SF-36 items and is composed of six multi-level dimensions: physical functioning, role limitations, social functioning, pain, mental health and vitality.

## Statistical analysis

Primary analyses will be conducted on an intention-to-treat basis, all participants will be included regardless of whether they completed the follow-up assessment visit. To handle missing data, we will use methodology based on last observation carried forward for participants who did not attend the post-assessment visit. The mean change between pre-intervention and post-intervention measures will be analyzed using the *t*-test when change data are normally distributed otherwise the nonparametric Wilcoxon matched-pairs signed-rank test will be used. Mixed-model analysis will be used to evaluate the change of weight during the intervention to control for relevant covariates. Analyses will be carried out using the SPSS statistical package.

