# February 16, 2018

Inclusion from HAI over 6 month (approximately 400 individuals in total) with about 50 % of the cohort meeting the inclusion criterion generates close to 200 subjects. With a modest assumption of participation rate of 50%, this leave 100 individuals to be randomized into a control group or an intervention group (n=50 per group). For the selected cohort with central obesity in HAI, the mean and SD for VAT-mass is  $2905 \pm 817$  g for men and  $1620 \pm 538$  g for women. Preliminary power calculations based on a 20% decrease in VAT mass,  $\alpha=0,05$  and  $\beta=0.8$  concludes that each group needs to consist of at least 33 subjects for men and at least 45 women. As we will analyze the %-change in VAT over time, we do not need to separate the analysis on sex and thus, there should be enough power to detect the above mentioned changes in VAT mass.

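### With VAT measured once before and once after, LOCF enters 0% change for every non-attender; the primary comparison then rests on an unstated assumption and can be biased in either direction

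*Combined protocol and SAP*

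**What the plan says.** The primary outcome is "Visceral adipose tissue as measured by DXA". The Statistical analysis section sets an intention-to-treat analysis in which "all participants will be included regardless of whether they completed the follow-up assessment visit". For those without a post-assessment, "we will use methodology based on last observation carried forward for participants who did not attend the post-assessment visit".

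On the test itself: "The mean change between pre-intervention and post-intervention measures will be analyzed using the" t-test, or the Wilcoxon matched-pairs signed-rank test if the changes are not normally distributed. The text does not say whether the t-test compares the arms or tests change within an arm.

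The sample-size paragraph that follows fixes the scale: "As we will analyze the %-change in VAT over time, we do not need to separate the analysis on sex". It also fixes the size: "this leave 100 individuals to be randomized into a control group or an intervention group (n=50 per group").

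A mixed model appears once, for another outcome: "Mixed-model analysis will be used to evaluate the change of weight during the intervention to control for relevant covariates".

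The plan gives no expected non-attendance, no reason for choosing LOCF and no sensitivity analysis. No interim DXA is described; the only samples with an intermediate time point are stool samples (section on stool sample processing).

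**The concern.** LOCF needs an earlier post-baseline value to carry forward. Here the text describes none for VAT, so the carried value is the baseline and the %-change is exactly zero. The analysis treats that zero as an observation. The primary estimate and its interval then depend on how many people miss one visit, and on the unstated assumption that those people did not change.

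Equal attendance cannot be taken for granted. One arm trains "three times a week for 10 weeks and each session will last for 45-60 min"; the other waits and is offered training afterwards (Clinical relevance section). Some fall in VAT in both arms is also possible, because all participants of the parent study receive lifestyle counselling. The documents do not give its size.

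**Working it through.** **1. The plan's own figure.** Inputs from the sample-size paragraph: mean and SD 2905 and 817 g (men), 1620 and 538 g (women), 20% decrease, α = 0.05, power 0.80. (The text writes β = 0.8; only a power of 0.8 reproduces its result.)
- Men: 0.20 × 2905 = 581 g; 581/817 = 0.711. A two-sided two-sample t-test needs 32.03, so 33 per group.
- Women: 0.20 × 1620 = 324 g; 324/538 = 0.602. It needs 44.26, so 45 per group.

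Both stated figures are reproduced, with no term for missing data.

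**2. The bias.** In one arm, let f be the missing share, O the attenders' mean %-change and m the non-attenders' true mean %-change.
- True arm mean: (1 − f)·O + f·m
- LOCF arm mean: (1 − f)·O + f·0
- Bias within an arm: −f·m
- Bias in training minus control: −(f_T·m_T − f_C·m_C)

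The between-arm bias is zero only if the two products are equal. Equal attendance is not enough. If data are missing completely at random with equal f, then m = O in each arm and LOCF returns (1 − f) times the true difference.

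**3. Numbers.** The missing shares and mean changes are assumptions. Each pair is training/control; differences are training minus control, in percentage points.

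| Missing % | Attenders | Non-attenders | True | LOCF | Bias |
|---|---|---|---|---|---|
| 5/5 | −20/0 | −20/0 | −20 | −19 | +1 |
| 10/10 | −20/0 | −20/0 | −20 | −18 | +2 |
| 20/20 | −20/0 | −20/0 | −20 | −16 | +4 |
| 30/30 | −20/0 | −20/0 | −20 | −14 | +6 |
| 20/20 | −20/0 | 0/0 | −16 | −16 | 0 |
| 20/20 | −20/0 | +5/0 | −15 | −16 | −1 |
| 30/10 | −10/−10 | −10/−10 | 0 | +2 | +2 |
| 10/30 | −10/−10 | −10/−10 | 0 | −2 | −2 |

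Example, sixth row: true = 0.8 × (−20) + 0.2 × 5 − 0 = −15; LOCF = 0.8 × (−20) − 0 = −16.

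**4. Intervals and error rate.** Simulation with 20,000 trials per cell, 50 per arm and a pooled t-test. Log-VAT SD is 0.31, between 817/2905 = 0.28 and 538/1620 = 0.33. Pre-post correlation r is 0.5/0.7/0.9, which the documents do not give.
- True effect 20 points, non-attenders like attenders: coverage of the 95% interval is 94.5/94.3/93.1% at 5% missing, 93.2/91.8/87.1% at 10%, 87.0/82.5/64.9% at 20%, and 75.9/65.3/33.0% at 30%.
- Within the training arm only, 20% missing: 80.7/70.3/42.2%.
- No effect, common 10% fall: type I error is 7.0/8.3/13.5% with 30% v 10% missing, and 5.6/5.7/7.0% with 20% v 10%.
- No effect, common 5% fall, 30% v 10% missing: 5.5/5.6/7.1%.

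**5. The alternative under the same test.** ANCOVA of %-change on arm and baseline, in participants with a post value, assumes that data are missing at random given arm and baseline. At 20% missing with attenders at −20% v 0%, it estimates 20 points whatever the non-attenders did.
- Truth 20: coverage about 95%.
- Truth 16 (non-attenders unchanged): 89.6/86.6/70.3%, against about 95% for LOCF.
- Truth 15 (trained non-attenders gained 5%): 86.3/81.4/57.9%, against 94.7/94.5/93.9% for LOCF.

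If trained non-attenders changed by X and control non-attenders by 0, the absolute bias is 0.2·|X| for LOCF and 0.2·|X + 20| for ANCOVA. The two are equal at X = −10.

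**The case against.** The strongest reply is that replacing LOCF swaps one uncheckable assumption for another. By step 5, LOCF is closer to the truth whenever trained non-attenders achieved less than half the attenders' fall, which is plausible for people who stop training. This stands. It rules out an observed-data analysis alone as the remedy and makes the sensitivity analyses a requirement.

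Four further points stand in part.
- The single post measure is inferred. An interim DXA would remove the exact zero, but the text describes none.
- The bias formula is for a difference in means and does not cover the signed-rank branch, which in its usual form drops zero differences. That branch could often apply: under the same model at 20% missing, a Shapiro–Wilk test on the training arm's LOCF changes rejected normality in about 53–78% of trials. The plan names no normality test.
- The lowest coverages and the 13.5% error rate need r = 0.9, and the latter also needs threefold unequal attendance. The milder null cases give about 5.5–7%.
- Analysing attenders only would sit badly with the plan's statement that everyone is included, and a model in grams would lose the reason for pooling the sexes.

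A reader might infer that LOCF is safely conservative here, or that it must understate the benefit. The documents support neither: the direction depends on what non-attenders did, and the plan has no information on that. A reader might also infer that LOCF leaves the trial short of power. That does not follow. The plan states no attrition allowance, but 50 per group exceeds the 33 and 45 required. For a 20-point effect with 20% missing and non-attenders like attenders, LOCF power is 86/97.5/100%.

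**Conclusion.** The concern holds as a defect in how the primary analysis is specified, and it should be corrected before analysis. As the text describes VAT measurement, LOCF fixes every non-attender at 0% change. In the between-arm t-test, the resulting bias vanishes only if missing share times non-attenders' mean change is equal in the two arms. When training works, it is present even if data are missing completely at random.

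The size cannot be derived from the documents, which give neither non-attendance nor the pre-post correlation. Under the assumptions shown, it runs from 4 points too small to 1 point too large at 20% missing per arm. It is about 1 point of 20 at 5% missing. It becomes material at about 20% missing or with clearly unequal attendance. What is certain is the mechanism and the absence of any analysis that would reveal its effect.

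**What to change.** - **Primary analysis.** Specify a between-arm mixed model of log VAT with pre and post values, a common baseline mean and an arm-by-time effect. Include every randomised participant with a baseline value. Back-transform to a ratio or %-change, so that the sexes can still be pooled as the plan intends. State the missing-at-random assumption.
- **Data collection.** Ask all randomised participants, including those who stop training, to attend the post DXA. Report non-attendance by arm.
- **Sensitivity analyses.** Report LOCF, labelled as zero change, beside a delta-adjusted grid by arm. Set the non-attenders' mean change to the attenders' mean, half of it, zero, and a gain. With attenders at −20% v 0% and 20% missing, 0.8 × (−20) + 0.2 × X for X = −20, −10, 0 and +5 gives effects of 20, 18, 16 and 15 points (the 5% gain is illustrative). Base the conclusion on whether it holds across that range.

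**Cost.** SAP wording and minor SPSS programming; a mixed model is already planned for weight. Under missing at random, the effect is overstated if non-attenders changed less than attenders: 20 v 16 points if unchanged, 20 v 15 if trained non-attenders gained 5%, at 20% missing. The model keeps non-attenders in the analysis but obtains no post-intervention information from them. For ANCOVA of %-change, which rests on the same assumption (the log model was not simulated), the standard error relative to LOCF is −3% to +3% at 10% missing, 8–12% larger at 20% and 20–26% larger at 30%. Power for a 20-point effect at 20% missing, with non-attenders like attenders, is 94/99/100% at r = 0.5/0.7/0.9, no lower than under LOCF.
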